## 10 Participant risk management and safety

The Bariatric Surgery Registry is an observational and epidemiological study collecting data at the time of procedure or from medical records and is unlikely to result in any harm to participants.

Participants who are contacted by telephone for follow-up information may experience minimal discomfort related to anxiety answering personal questions related to their weight, health and medical procedures. The Registry's staff are trained to minimise their distress.

It is not unusual that a participant may not want anyone to know that they have undergone a bariatric surgical procedure and this will be evident if it is made known that they participate in the Bariatric Surgery Registry. This could cause the participant to become upset or aggrieved. The likelihood of harm occurring is perceived to be very low as evidenced by the Registry's low opt out rate which has remained at less than 4% since it began in 2012. Of the participants who have contacted the Registry or ethics committees to complain and/or express their emotional distress when they receive their Participant Fact Sheet, the severity has not been demonstrated to be beyond the level of discomfort. No consequences of any discomfort have been made known to the Registry.

Participants are advised of the low risks associated with participating in the Participant Fact Sheet as well as the indirect benefits of participating in such a registry. Indirect benefits of participating in the research include the monitoring of the quality of care provided by hospitals, surgeons, and gastroenterologists; the delivery of the best possible health service to people undergoing bariatric surgery can be ensured; and, participants can be notified if a significant issue is identified with the medical device or procedure.

## 11 Data analysis

### 11.1 Process of data analysis

Non-identifiable data is provided to an independent biostatistician by secure file transfer for review on a 6 monthly basis.

The results are provided to the Registry's Programme Manager. Only Monash University Registry staff, who are non-clinical, have access to identifiable data. All data used in reports and/or publications is cleaned, de-identified and verified prior to analysis. Routine re-analysis of data is undertaken by the Programme Manager to ensure findings are reproducible.

### 11.2 Case-mix (risk) adjustment

Operative outcomes for each individual surgeon or gastroenterologist need to be interpreted with great care as the case-mix of surgical practice can vary. For example, some surgeons may only take on patients needing more difficult revision surgery while others may operate predominantly on higher risk patients having primary surgery. As a result, the comparison of outcomes must carefully consider the patient characteristics that are beyond the control of the surgeons or gastroenterologists. This typically will involve taking account of a participant's age, sex, body mass index (BMI) and the existence of any other co-morbidity.

Other confounders to be considered are the socioeconomic status (SES), demographic location and complexity of the surgery. In cases where clear exceptions exist, as identified by validated bio-statistical means, individuals may be excluded from sample data to ensure results are not misleading. Documentation of decisions to remove cases from samples for data analysis purposes is maintained by the Registry's Data Manager. The number and percent of such observations will be reported to the Steering Committee.

It is expected that this information will eventually be used for the development of a policy, which will be able to identify potential outliers.

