## 3.0 Introduction

### 3.1 Lay summary

Obesity is a prevalent disease in Australia and New Zealand. This is a major concern for both countries as obesity is an important risk factor for ill health. Obese persons are more likely to suffer from many other serious health conditions including diabetes, heart disease, liver disease, infertility, stroke and cancer. As a consequence, people who are obese are more likely to have a reduced life expectancy.

Lifestyle interventions have not been found to be effective in providing a long-term solution for the treatment of obesity. When conservative weight loss measures tried by those with obesity are not successful, weight loss or ‘bariatric,’ surgery may be considered.

Bariatric surgical procedures are operations performed with the intention of helping people with obesity achieve and sustain weight loss. Weight loss following bariatric surgery leads to significant improvement in health and well-being. Individuals who have the surgery are known to live longer. However, it is an invasive surgery with known surgical risks and potential side effects, which can be as severe as death. Given people are having this surgery to improve their health, it is critical that the surgery is performed with a minimum of side effects; otherwise, it cannot be justified.

The purpose of the Bariatric Surgery Registry (hereafter, Registry) is to monitor the safety of the surgery and to assess the long-term changes in the health of people who undergo bariatric surgery in Australia and New Zealand.

The Bariatric Surgery Registry collects data, or information, on the operation performed, who performed the operation, where the operation occurred, complications from the surgery, weight at various time points and diabetes status and management. It is necessary for the Registry to keep identifiable participant details, such as their name, date of birth, address and Medicare number (Australia) or National Health Index (NHI) number (New Zealand), in order to track their progress through data linkage to other datasets.

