## 3.2 Background

Obesity poses a major public health challenge for Australia and New Zealand. According to the Australian Health Survey (2014-15), nearly 28% of the adult population are considered obese (defined as a BMI >30 kg/m^2) compared to 18% in 2004/05. Amongst those Indigenous Australians who regularly attend of Indigenous primary health care organisations, 42.9% are obese. In New Zealand, the rate of obesity has been increasing by 1% every year since 1989 and as of the 2016/2017 Health Survey, 32.2% of the adult population (1,234,000 people aged over 15 years) are obese. Māori and Pacific Islands peoples have the highest incidence of obesity with rates of 50% and 69%, respectively for adults (aged 15 years and over), and 18% and 29% for children (aged 2-14 years).

Obesity is a major risk factor for many preventable diseases including type 2 diabetes, heart disease, hypertension, stroke, cancer and musculoskeletal disorders. It can also significantly affect quality of life and shorten lifespan. As those with obesity may suffer from other chronic medical conditions, the cost of their healthcare is much greater than for those with a healthy weight. In 2010-11, the direct cost of obesity on the Australian economy was estimated to be AUS\$8.6 billion. A New Zealand study approximated the healthcare cost of obesity to be NZ\$722 million; and the cost of lost productivity was estimated to be NZ\$849 million. These figures demonstrate that the management of obesity demands to be a national priority for both countries.

Although lifestyle interventions can be effective in the short term, they are rarely durable in the long-term. Maintenance of weight loss for the long term is a challenge for those on lifestyle intervention programmes. For those with class II obesity (BMI>35kg/m^2), several Randomized Controlled Trials (RCT) and multiple case series suggest that bariatric surgery provides more predictable and durable weight loss than conservative regimes and is generally very safe.

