Since 2009, New Zealand has annually published 'Clinical Guidelines for Weight Management in New Zealand Adults', which continually review the current evidence and priorities for the prevention and treatment of obesity. These guidelines support the framework set out in the New Zealand Health Strategy and the He Korowai Oranga: Māori Health Strategy which guides health related services to achieve the best health outcomes for Māori. The 2009 Guidelines noted that there was no evidence of bariatric outcome data by ethnicity, demonstrating the public's need for this information.

The New Zealand Ministry of Health guidelines 'Weight Management for Adults' suggests considering bariatric surgery for people with Class II obesity with another significant disease. Public funding for bariatric surgery is available from the Ministry of Health for individuals who meet set criteria. A review of publicly funded bariatric surgery by Rahiri et al (2017) suggested that there may ethnic disparities in the rate of access to public funded procedures.

Bariatric surgery is burgeoning in Australia. The number of separations for bariatric surgery reported by the Australian Institute of Health and Welfare (AIHW) for 2014-15 was 22,713. The Medicare Benefits Schedule (MBS) data for 2017 indicates the number of procedures has grown to over 26,000 procedures per year however, this only reflected approximately 1.4% of the Australian morbidly obese having bariatric surgery as an intervention. The AIHW reported an additional 124,600 bariatric surgery-related procedures were billed to Medicare during the 2014-2015 period, with a total cost estimated at \$62.8 million for all Medicare billed procedures.

In New Zealand, figures show that 889 bariatric procedures were performed for the year ending 2014, representing 0.04% of those with a BMI >40. The Ministry of Health has committed over \$30 million since 2014 for bariatric surgery for individuals who meet set criteria and additional funding has also been made available by local district health boards to support publicly funded procedures. In 2017, approximately 480 people were able to access publicly funded bariatric surgery of amongst at least 210,000 individuals who could be eligible.

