### 8.4.2.2 Data collected from ICD-10-AM coding reports (or similar hospital discharge reports)

Hospital Information Services (HIS) at each hospital site, or of a private hospital group, are to provide regular ICD-10-AM coding reports (or similar discharge reports) for bariatric procedures performed by surgeons or gastroenterologists who participate in the Registry. The coding reports include patient demographic and procedure information. In Australia, these reports are sent to the Registry using a secure file transfer platform (SFTP). In New Zealand, these reports are sent to UniServices in accordance with the agreed Memorandum of Understanding for each site.

The ICD-10-AM coding (or similar) reports provided by HIS are used to verify data submitted to the Registry. The reports confirm the procedures already submitted and allow Registry staff to identify those which have not. Surgeons, gastroenterologists and hospital data collectors will be asked to provide the remaining clinical information for the patients whose procedures were identified in the coding report:

- device/stapling information;
- whether the operation was a primary or revision;
- height/weight information;
- diabetes status and treatment; and
- perioperative follow-up data is also requested for efficiency.

Patients whose details are obtained from these reports are sent a PFS and the opt-out approach is followed according to the process described in section 8.3. Once the opt out period has passed, if the request for the missing data elements from the surgeon or gastroenterologist was not met, Registry staff will contact the participant to collect the required information.

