### 8.4.3 Data elements

Data elements are defined in the Registry's data dictionary and governed by the Steering Committee, with any changes managed through a data element variation process.

The data elements collected include:

- **Patient data elements:**

*Patient Identifiers:*

- full name;
- address;
- date of birth;
- UR number/hospital (and IHI numbers when available); and
- email address (if supplied by patient)

- **Patient demographic information:**

- Medicare number (Australia only)
- Department of Veterans Affairs (DVA) number;
- NHI number (New Zealand only);
- phone numbers;
- gender; and
- indigenous status (Australia)/ethnicity (New Zealand)

- **Operation data elements:**

*Clinical details:*

- start weight (for primary participants only);
- day-of-surgery (DOS) weight;
- height;
- diabetes status and treatment; and
- concurrent renal and liver transplant

*Procedural information:*

- surgeon name;
- procedure date;
- procedure type;
- surgical approach used (open, laparoscopic, robotic)
- primary/ revision;
- planned or unplanned revision status;
- reason for revision;
- bariatric procedure prior to revision;
- if the procedure was abandoned;
- reason for abandoning procedure;
- length of hospital stay; and
- mortality status including date of death and whether the death was likely to be related to the bariatric procedure

*Device or Staple details:*

- type;
- brand;
- model;
- port fixation method; and
- buttress

- **Follow-up data elements**

*Elements for Perioperative (up to 90 days post-surgery) Data:*

- date participant had a post-operative review
- occurrence of unplanned return to theatre and reason/ complication occurrence of unplanned admission to intensive care and reason/ complication;
- occurrence of unplanned re-admission to hospital and reason/ complication;
- prolonged hospital stay and reason/ complication; and,

- mortality status including date of death and whether the death was likely to be related to the bariatric procedure

*Elements for Subsequent Clinical Data of Primary Participants (collected annually for ten years):*

- weight;
- diabetes status and treatment;
- re-operation and reason; and
- mortality status including date of death and whether the death was likely to be related to the bariatric procedure

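### Does the case-mix section rely on co-morbidity data that the Registry does not list?

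*Protocol*

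**What the plan says.** Section 11.2 (Case-mix (risk) adjustment) explains that outcomes of individual operators must be read with care because their patients differ. It says that allowing for this typically means accounting for age, sex, "body mass index (BMI) and the existence of any other co-morbidity". It then names socioeconomic status, location and complexity of surgery as further confounders to consider.

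Section 8.4.3 (Data elements) sets out what is collected. The clinical details recorded with the operation are start weight, day-of-surgery weight, height, diabetes status and treatment, and "concurrent renal and liver transplant". The list is introduced as what the elements *include*. The definitions are said to be in the Registry's "data dictionary and governed by the Steering Committee, with any changes managed through a data element variation process".

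Section 3.1 (Lay summary) describes the health information collected as "complications from the surgery, weight at various time points and diabetes status and management". Section 8.4.2.2 says that operators and hospital data collectors "will be asked to provide the remaining clinical information for the patients whose procedures were identified in the coding report"; the only disease in the items that follow is diabetes.

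Section 12 (Monitoring of outcomes) has the Steering Committee review the risk adjustment model until the data are mature enough for an outlier policy.

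**The concern.** An analysis plan can choose among covariates but cannot create one that was never recorded. If the Registry records diabetes and little else, a reader of 11.2 would credit the model with more adjustment than it can make. That would matter because section 5.0 promises risk-adjusted comparative outcomes and section 3.1 says the Registry will help identify surgeons, hospitals and procedures that fall below standard. An operator who takes sicker patients could look worse than the care deserves.

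The protocol's own background adds to the worry. It says that "Obese persons are more likely to suffer from many other serious health conditions including diabetes, heart disease, liver disease, infertility, stroke and cancer", and elsewhere links obesity to "type 2 diabetes, heart disease, hypertension, stroke, cancer and musculoskeletal disorders". It also cites New Zealand guidance that "suggests considering bariatric surgery for people with Class II obesity with another significant disease", so co-morbidity may be part of the reason for operating, and BMI need not stand in for it.

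**Working it through.** The protocol gives no figure to reproduce here. The check is to set the factors in 11.2 against every place that says what is collected.

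**Factors in 11.2 against fields in 8.4.3**

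| Factor in 11.2 | Listed field in 8.4.3 |
|---|---|
| Age | Date of birth, with procedure date |
| Sex | Gender |
| BMI | Height; start and day-of-surgery weight |
| Other co-morbidity | Diabetes status and treatment; arguably concurrent transplant |

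**Other descriptions of the data**

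- Section 3.1: diabetes is the only disease named.
- Section 8.4.2.2: the coding reports carry demographics and procedures; the items then requested name diabetes only.
- Table 5, electronic medical record row: weight, diabetes status and treatment, further operations.
- Table 5, other rows: identifiers and, depending on the source, length of stay, procedure codes, readmissions, and date or cause of death. No diagnosis codes are named.

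So no general co-morbidity field beyond diabetes and transplant appears in the protocol. The observation behind the concern is accurate.

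**How far that goes**

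1. Section 11.2 speaks of what is typical. It does not specify a model. Read literally, *other co-morbidity* means disease besides the obesity that BMI measures, and diabetes is such a disease. The phrase is met in part.
2. Section 11.2 names considerations rather than database fields. Socioeconomic status is also named there and has no field of its own in 8.4.3.
3. Section 8.4.3 is an open list, with the definitions in the data dictionary. Section 16 lists that dictionary as a companion document. It is not shown, so its contents cannot be assumed in either direction.
4. The other descriptions are weaker evidence. Section 3.1 is a lay summary. Section 8.4.2.2 covers only what remains to be collected, and it leaves out transplant, which 8.4.3 does list. Table 5 is headed as examples.
5. Section 8.4.2.5 allows sub-groups to collect fuller data with approval.

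**A count that looks informative**

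Section 3.1 names 6 obesity-related conditions (diabetes, heart disease, liver disease, infertility, stroke, cancer). Section 3.2 names 6 (type 2 diabetes, heart disease, hypertension, stroke, cancer, musculoskeletal disorders). Four are shared: diabetes, heart disease, stroke and cancer. Distinct conditions: 6 + 6 − 4 = 8. Listed as a baseline field: 1 of 8 = 12.5%.

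This does not measure a gap in adjustment. Both sentences describe diseases associated with obesity and are not closed lists, and neither is offered as a set of surgical risk factors. Infertility, for one, is not an obvious one. The guidance on surgery for Class II obesity does not settle it either, since the further disease it refers to could be diabetes.

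**The case for a change.** The best case for a change is that this concerns what is collected, which the protocol itself fixes, and so is not a matter for an unseen analysis plan. Every list the protocol gives points the same way, and the Steering Committee ought to know what the model covers before it writes an outlier policy. A cross-reference from 11.2 to the recorded fields would cost one look-up and a phrase at the next amendment.

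The agreement between the lists stands, and so does the low cost. A cross-reference would be harmless tidying. The argument about an uncollected covariate, however, needs the premise that further co-morbidity is uncollected, and the protocol does not establish that. Whether 11.2 would need new wording at all turns on the dictionary: if it holds more fields, the sentence is right as written.

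A more specific rewrite could do harm. To write transplant in as a co-morbidity adjuster would settle a point the protocol leaves unclear, since it may be recorded as a concurrent procedure. To tie surgical complexity to procedure type or approach would be debatable, because these can be the operator's own choice, whereas 11.2 aims at patient characteristics outside the operator's control.

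**Conclusion.** The concern does not call for a change. Section 11.2 is broader than the fields printed in 8.4.3, but a hedged description and an open list do not contradict each other. Section 12 treats the risk adjustment model as provisional and under review. In practice the biostatistician will adjust for age, sex, BMI, diabetes and whatever else the dictionary defines, and the Steering Committee will see which covariates were used. New wording would not reduce confounding or alter any reported comparison.

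The size of any residual confounding cannot be given: the documents contain no co-morbidity prevalences, no variation between operators and no outcome rates by co-morbidity. The conclusion assumes that reports of risk-adjusted results will state which covariates were used, as is normal practice. Section 13.2 does not say that the individual surgeon reports are risk-adjusted, so nothing is inferred about them. If the dictionary did prove to hold nothing beyond diabetes and transplant, the absence of other co-morbidity would be a limitation to state when results are reported. It would still not be an error in this protocol.

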## 8.0 Study design

The Bariatric Surgery Registry is a population based, observational and epidemiological quality improvement study of persons with obesity who undergo bariatric surgery. Non-probability sampling is necessary as the Registry aims to capture the entire population.

Surgeons and/or gastroenterologists who are known to perform bariatric procedures are invited to participate in the Registry. Whilst their participation is voluntary, they are asked to sign a participation agreement stating that they have read the protocol and will maintain the responsibility for their patients’ data. All surgeons and gastroenterologists are provided with flyers and a poster for the recruitment of Registry participants using the opt out approach. They are also given **The BSR-i User Manual for Surgeons and Staff** and when requested, paper data forms for submitting their patient and operation information.

Those submitting data directly on the Registry’s web-based interface, the BSR-i, will be given a user ID and temporary password. **The BSR-i User Manual for Surgeons and Staff** contains an authorisation form to record anyone who enters information regarding patients on the behalf of surgeons or gastroenterologists. Data collectors in public hospitals who enter data on the BSR-i are provided with their own account and are able to submit data for each of those hospitals’ surgeons and gastroenterologists that participate in the Registry.

Private and public hospitals in Australia and New Zealand that care for persons who have or had bariatric surgery will be contacted to participate in the Registry. Ethics approval and site or locality approvals are to be sought for each hospital. A Memorandum of Understanding between Monash University and each hospital/hospital group representative should be executed prior to the commencement data collection at the hospital(s). Once these steps have been taken and all approvals has been granted for the hospital’s or hospital group’s participation, Registry staff will contact the person at the hospital responsible for discharge coding. A template will be provided to the coder along with access to a secure file transfer platform to send the coding reports to the Registry.

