## 8.1 Participant eligibility

Anyone who undergoes bariatric surgery as treatment for obesity in Australia or New Zealand is eligible for inclusion for the study (non-probability sampling). The minimum age for eligibility is set at 2 years and a maximum age of 95 years.

[figure not shown]
The study population may include:

- children or young persons;
- persons with a cognitive impairment;
- people highly dependent on medical care;
- persons who cannot speak English; and/or
- persons who identify as Aboriginal, Torres Strait Islander peoples, Māori or Pacific Islands peoples.

Pregnant females are not considered for bariatric surgery and are therefore excluded from the study.

**Figure 1** illustrates the overall recruitment process for the participation of hospitals, surgeons, gastroenterologists and bariatric patients in the research.

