A secure file is kept of individuals who opt out and this file is strictly accessible to Registry staff only. All health information for those who opt out is deleted and/or destroyed, if in paper form, in accordance with the National Statement for Ethical Conduct in Human Research 2007 (2018). The information kept in the secure file is only that which is needed to ensure the individual will not be contacted again about their procedure, including their name, date of birth, name of the treating surgeon or gastroenterologist and hospital. When individuals contact the Registry to opt out, they will be asked for their verbal consent for this information being kept for this purpose. This retained information validates that the procedure was submitted, ensuring and verifying that surgeons are not selectively enrolling participants. Furthermore, the file allows for accurate reporting of participant opt-out and withdrawal rates, preventing the Registry from reporting a false opt out rate.

If a PFS is returned in the mail, Registry staff will attempt to validate the address used. If a corrected and current address cannot be obtained, all information related to the patient will be deleted and securely destroyed, if in paper form, as the opt out approach is not able to be completed.

**Figure 2** illustrates the typical participant recruitment process as well as recruitment and data verification using the information collected from the hospital discharge reports.

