#### 8.4.4 Data quality

Data completeness and accuracy are optimised through routine in-built validation and completion checks in the Registry database to minimize data entry error. These include:

- data entry controlled by form logic and limited to feasible data;
- use of built in edit checks to ensure data meets the required formats and range;
- accuracy enhanced by the use of exhaustive drop down lists providing all possible answers to minimize free text entry where applicable;
- use of hide and show mechanisms to guide data entry to required fields;
- use of explanatory texts to assist data entry;
- validation rules applied at the time of submission with alerts to assist with errors and missing data; and,
- the use of a participant management system to list incomplete data and other actions required.

Additional quality checks post data entry includes checking for:

- duplicate data;
- missing data;
- data consistency; and
- data validity.

Data quality and completeness are checked at a number of stages of the data management process. Errors in data quality, when identified, may be referred back to contributing surgeons, gastroenterologists or hospitals for review.

Case ascertainment, as well as both brief and comprehensive audit processes, are performed on site by Monash University Registry staff (Australia only). Registry staff perform regular remote audit checks to verify the accuracy of data received from surgeons and gastroenterologists. This is done during the course of a follow-up phone call from the call centre or by Registry staff directly contacting surgeons' or gastroenterologists' rooms.

Completeness and accuracy of the eligible population captured by the Registry is assessed using hospital ICD-10-AM coding reports (or similar hospital discharge reports) provided by participating hospitals or hospital groups. Cross-checking with these reports allows for complete data capture at each hospital site and provides data validation for each procedure submitted by the surgeon or gastroenterologist. These reports are provided at regular intervals by the organisation's administrator and only contain data of participating surgeons and gastroenterologists.

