In Australia, periodic linkages are intended with other repositories, or datasets, of health information that can validate Registry data. The ICD-10-AM discharge report validations and other data linkages will ensure that all eligible patients are included in the Registry and minimise the risk of bias in data entry by contributing surgeons and gastroenterologists. The linkages will also verify critical quality data such as patient mortality, defined adverse events and other outcome measures are completely captured. Requests to link New Zealand Registry data to national data sets will be considered by the Steering Committee on a case-by-case basis. For data linkages in Australia and New Zealand, the necessary approvals from an HREC/HDEC will be sought when required. Examples of repositories, their role in data validation, and what information will be collected and disclosed by the Registry are described in **Table 5**.

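### Section 11.2 lets valid, eligible cases be left out of surgeon comparisons because they are statistically unusual, without confirmed error or ineligibility and without a stated result that keeps them in (minor)

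*Protocol*

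**What the plan says.** Section 11.2 explains that clinicians' results must be compared with allowance for age, sex, BMI, co-morbidity, socioeconomic status, location and complexity of surgery. It then opens an exception: "In cases where clear exceptions exist", and "as identified by validated bio-statistical means, individuals may be excluded from sample data to ensure results are not misleading". The sentences that follow speak of cases and observations, so the individuals are patients or procedures, not clinicians.

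Two safeguards are attached. The Data Manager keeps a record of the decisions, and "The number and percent of such observations will be reported to the Steering Committee". The section expects this information eventually to support a policy for identifying outliers.

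Suspect data have a separate route. Under 8.4.4, "Errors in data quality, when identified, may be referred back to contributing surgeons, gastroenterologists or hospitals for review". Under 11.1, data are cleaned and verified before analysis.

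On coverage, section 8.0 says "Non-probability sampling is necessary as the Registry aims to capture the entire population", and 8.1 says "Anyone who undergoes bariatric surgery as treatment for obesity in Australia or New Zealand is eligible for inclusion for the study". Section 8.3.1 keeps minimal details of people who opt out, partly for "ensuring and verifying that surgeons are not selectively enrolling participants". Section 8.4.4 says that discharge reports and linkages "will ensure that all eligible patients are included in the Registry and minimise the risk of bias in data entry".

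**The concern.** The trigger in 11.2 is statistical. Errors are handled in 8.4.4 and verification precedes analysis, so the permission reaches records that are correct and eligible but unusual. The definition of an exception and its threshold may properly sit in an analysis plan. The permission itself is fixed in the protocol, and a plan that follows the protocol may use it.

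For an infrequent yes/no outcome, the unusual record is often the complication itself, above all a complication in a low-risk patient. If such records can be dropped because a model finds them surprising, selection that the Registry works to prevent at enrolment could return at analysis. What is at stake is the count of events, and the observed rates, on which surgeon comparisons and the later outlier policy would rest.

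**Working it through.** The protocol gives no event rate, exclusion rate or method for this point, so there is no figure to reproduce. The rates below are assumptions, shown as a range.

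**1. Which records look extreme.** Let p be a patient's predicted risk.
- Pearson residual: event √((1−p)/p); non-event −√(p/(1−p)).
- Deviance residual: event √(−2 ln p); non-event −√(−2 ln(1−p)).
- At p = 0.05, Pearson gives √(0.95/0.05) = 4.36 and −√(0.05/0.95) = −0.23. Deviance gives 2.45 and −0.32.
- For any p below 0.5, an event exceeds 1 in absolute value on the Pearson scale (1.18 on the deviance scale) and a non-event falls below it. If all predicted risks are below 50%, ranking by absolute residual therefore puts every event ahead of every non-event.

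**2. Events lost when the largest residuals are removed.** With event rate r and excluded fraction x < r, the share of events lost is x/r and the rate afterwards is (r−x)/(1−x). For x = 1%:

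| r | Events lost | Rate after |
|---|---|---|
| 3% | 1/3 = 33.3% | 2/99 = 2.02% |
| 5% | 1/5 = 20.0% | 4/99 = 4.04% |
| 8% | 1/8 = 12.5% | 7/99 = 7.07% |
| 10% | 1/10 = 10.0% | 9/99 = 9.09% |

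Removing 1% without relation to outcome loses about 1% of events. Either way, the Steering Committee would be told 1%.

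**3. How far the answer depends on the rule.** A simulation assumed 100 surgeons with 100 procedures each, 10 surgeons with an odds ratio of 2.5, four normal covariates, a 20% revision indicator and a logistic case-mix model. Baseline risk was 5%, and the crude event rate came to 5.65%.
- Most extreme 1% of covariate profiles: 1.3% of events lost. Most extreme 2%: 2.5%.
- Largest 1% of residuals: 17.7% of events lost, no non-events lost, rate down to 4.69%. Mean predicted risk was 3.0% in the lost events against 7.8% in all events, so complications in low-risk patients go first.
- |Pearson| > 3 catches an event when (1−p)/p > 9, that is p < 0.10. It dropped about 76% to 84% of events, depending on the assumed covariates.
- |Deviance| > 3 catches an event only when p < e^(−4.5) = 0.011. It dropped 0.1%.

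**4. Effect on the adjusted ratio.** The average observed/expected ratio of the poor performers went from 2.01 to 1.99 (largest 1% of residuals) and to 1.94 (|Pearson| > 3). It is stable because expected counts fall along with observed ones when the model is fitted to the reduced data. If expected counts were instead kept from the full data, and poor performers lost the average 17.7% of events, the ratio would be about 2.01 × 0.823 = 1.65. The protocol does not say which would be done.

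**The case against.** The strongest reply is that the protocol never mentions residuals. The permission follows directly on a list of confounders, so exclusion on covariate profile is the natural reading, and that does little harm. One may also doubt that trimming the events of an infrequent outcome would count as a validated method. This stands: step 2 shows what the wording allows, not what the Registry intends, and the spread in step 3 reflects the choice of rule.

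A reader might infer three stronger claims that the documents do not support.

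- *That 11.2 contradicts 8.0, 8.1, 8.3.1 and 8.4.4.* It does not. Those sections govern enrolment and data capture, and excluded cases stay in the Registry.
- *That poor performers would escape detection.* With the model refitted, their ratio hardly moves. Larger effects can be produced: with 200 cases, a 2% registry rate and a 5% surgeon rate, removing 2 event cases cuts the chance of a flag from 67% to 42% (exact one-sided binomial test at 0.025). That assumes that every excluded case is an event, that all belong to one surgeon, and that the benchmark is unchanged. The protocol supports none of these.
- *That exclusions are unsupervised.* Section 11.1 provides six-monthly review of the data by an independent biostatistician and routine re-analysis by the Programme Manager. Section 12 has the Steering Committee review the risk adjustment model and its performance. Neither requires a result with the cases kept in, but both are real oversight.

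The consequence is also not immediate. The outlier policy is still to come, and 13.2 neither says that individual surgeon reports apply these exclusions nor ties the adverse-event and mortality figures in progress reports to them. A very large loss of events would probably be noticed. Finally, an analysis plan not at hand may add an all-cases result, so the lack of one is the weaker half of the point.

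**Conclusion.** The point holds as a minor weakness in a discretionary rule. Section 11.2 permits correct, eligible cases to be left out of surgeon comparisons on a statistical trigger, and its own safeguards neither confine this to error or ineligibility nor show what kind of case was removed. The size cannot be fixed from the protocol. It runs from next to nothing under a covariate or strict deviance rule to between a tenth and a third of events for a 1% residual-based exclusion, assuming event rates of 10% down to 3% and all predicted risks below 50%. The loss would be in event counts and observed rates. The observed/expected ratio would stay nearly unchanged provided the model is refitted to the reduced data. None of this is an estimate of harm that has occurred or is expected.

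**What to change.** Replace the permission in 11.2 with wording such as:

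> The main comparisons include all eligible procedures, apart from restrictions fixed in advance on recorded baseline or procedural characteristics and applied without regard to outcome or surgeon. Statistically unusual records trigger verification through 8.4.4 and are corrected or removed only for confirmed error or ineligibility. Any analysis with statistical exclusions is a labelled sensitivity analysis shown beside the main result, with the excluded cases tabulated by outcome and by (de-identified) surgeon for the Steering Committee.

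The allowance for restrictions fixed in advance is needed so that the text does not bar legitimate ones on items listed in 8.4.3, such as concurrent renal or liver transplant. The cost is one paragraph and a small extra verification and reporting workload. No new data are needed. It is best done before information from 11.2 is used for the outlier policy.
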